6.2. Secondary Endpoint(s)

6.2.1. Pharmacokinetic Analyses

PK parameters for PF-06823859 following single-dose administration will be derived from the serum concentration-time profiles using noncompartmental methods, as data permit.

The PK parameters will be summarized descriptively by treatment group in accordance with Pfizer data standards, as data permit. Missing values will be handled as detailed in Section 5.3. Each PK parameter will be summarized by treatment group and will include the set of summary statistics as specified in the table below:

Table 4. PK Parameters to be Summarized Descriptively

Parameter	Summary Statistics
C_{\max} , C_{\max} (dn), AUC_{inf} , AUC_{inf} (dn), AUC_{last} , AUC_{last} (dn), $AUC_{14\text{day}}$, $AUC_{28\text{day}}$, MRT, V_{ss} , CL	N, arithmetic mean, median, standard deviation (SD), percent coefficient of variation (%CV), minimum, maximum, geometric mean and geometric %CV.
T_{\max}	N, median, minimum, maximum
$t_{1/2}$	N, arithmetic mean, median, SD, %CV, minimum, maximum.

dn: dose normalized

There will be summary tables presenting all PK parameters.

To assess the relationship between the PK parameters and dose, dose normalized AUC_{inf} , AUC_{last} and C_{\max} will be plotted against dose, and will include individual participant values and the geometric means for each dose. Geometric means will have a different symbol than the individual values. The values will be dose normalized (to a 1 mg dose) by dividing the individual values and raw geometric means by dose. A footnote will be added to the plots to indicate that geometric means are presented and that data from both cohorts are presented on the plot.

Supporting data from the estimation of $t_{1/2}$ and AUC_{inf} will be listed by analyte where applicable: terminal phase rate constant (k_{el}); goodness of fit statistic from the log-linear regression (r^2); the percent of AUC_{inf} based on extrapolation ($AUC_{\text{extrap}\%}$); and the first, last, and number of time points used in the estimation of k_{el} . This data may be included in the clinical study report.

PFIZER GENERAL BUSINESS

Presentations for PF-06823859 concentrations will include:

- a listing of all concentrations sorted by subject ID, cohort, dose and nominal time postdose. The concentration listing will also include the actual times. Deviations from the nominal time will be given in a separate listing.
- a summary of concentrations by dose and nominal time postdose, where the set of statistics will include n, mean, median, SD, %CV, minimum, maximum and the number of concentrations above the lower limit of quantification.
- median concentrations time plots (on both linear and semi-log scales) against nominal time postdose by dose (all treatments on the same plot per scale, based on the summary of concentrations by dose and time postdose).
- mean concentrations time plots (on both linear and semi-log scales) against nominal time postdose by dose (all treatments on the same plot per scale, based on the summary of concentrations by dose and time postdose).
- individual concentration time plots by dose (on both linear and semi-log scales) against actual time postdose (there will be separate spaghetti plots for each dose per scale).
- individual concentration time plots by participant (on both linear and semi-log scales) against actual time postdose [there will be separate plots for each participant (containing all doses) per scale].

The length of time used for the x-axes of these plots will be decided on review of the data, and will depend on how long PF-06823859 concentration is quantifiable in the matrix.

[figure not shown]
For summary statistics, median and mean plots by sampling time, the nominal PK sampling time will be used, for individual participant plots by time, the actual PK sampling time will be used.

6.2.2. Immunogenicity Endpoints

The incidence of the development of ADA and NAb will be listed and summarized for participants in the immunogenicity analysis set. Presentations for immunogenicity will include:

- Summary of ADA and NAb by sample
- Summary of ADA and NAb incidence over time
- Summary of incidence of ADA and NAb by dose and time postdose
- Summary of cumulative incidence of ADA and NAb by dose and time postdose
- Impact of ADA and NAb status on PF-06823859 concentrations

PFIZER GENERAL BUSINESS

- Summary of participants with ADA negative and PK > assay tolerance value at last sampling point

Immunogenicity assay titers will be used to determine incidence for ADA and NAb. Titer values will also be listed.

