COVID-19 questionnaire ^h	X	X									X	X	X	X	X	X	X	X
COVID-19 testing ⁱ	X									X								
COVID-19 check temperature ^j	X	X	X			X	X	X	X	X	X	X	X	X	X	X	X	X
PK blood sampling			X	X ^k	X	X	X	X	X		X	X	X	X	X	X	X	X
Immunogenicity (ADA, NAb) ^l		X									X	X		X	X	X	X	X
CCI																		
Urine drug testing	X	X																
Urinalysis (after ≥4 hour fasting)	X	X						X			X	X	X	X		X	X	X

PFIZER CONFIDENTIAL

Visit Identifier ^a Abbreviations used in this table may be found in Appendix 8 .	Screening	CRU Confinement							Follow-Up							ET			
		-28 to -2	-1	1		2	3	4	5	8	15	29	43	57	71	99	127	157	
Days Relative to Day 1	-28 to -2	-1		1		2	3	4	5	8	15	29	43	57	71	99	127	157	-
Visit Window (days)	-	-		-		-	-	-	-	±1	±3	±3	±3	±3	±3	±3	±3	-	
Hours After Dose			0 ^b	1	2	6	12	24	48	72	96	-	-	-	-	-	-	-	

- a. Day relative to start of study intervention (Day 1).
- b. Pre-dose (except for study intervention administration)
- c. Physical examination may be performed at non-specified timings if there are findings during the previous examination or new/open AEs, if appropriate and at the discretion of the investigator.
- d. Chest X-ray or other appropriate diagnostic image (ie, CT or MRI) results within 12 weeks prior of the screening visit, otherwise a chest X-ray must be performed and results obtained prior to dosing in the study. See [Section 8.2.2](#).
- e. Participants should be monitored from start of study intervention infusion until the end of infusion to assess the infusion site. See [Section 8.2.5](#).
- f. Participants who are HBsAg negative, HBcAb negative and HBsAb positive without unequivocal documentation of prior HBV vaccination or who are HBsAg negative, HBcAb positive and HBsAb positive are required to undergo HBV DNA reflex testing at screening. If HBV DNA is undetectable in the HBV DNA reflex testing at screening and the participant is enrolled the study, HBV DNA testing must be performed on Day 71, 157 and ET. See [Section 8.2.6.1](#).
- g. Additional TB testing is allowed at any time if requested by the investigator and/or if there is a suspicion of TB reactivation or new TB infection. See [Section 8.2.7](#).
- h. Check exposure to positive subject, residence or travel in area of high incidence and COVID-19 related signs and symptoms. To be done at least 2 days before and at each visit.

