2.2.2.1. Safety

Data from Study C0251001 suggests that PF-06823859 was generally well tolerated and safe when given up to 2000 mg as single IV dose and up to 1800 mg given 600 mg IV Q2W × 3. The most common AE was upper respiratory tract infection, likely due to viral infection. No serious AE or death occurred during the study.

During the SAD period, all TEAEs reported were mild in severity. During the MAD period, while the majority of the TEAEs were mild in severity, 4 TEAEs were moderate in severity: 2 TEAEs (abdominal pain upper and headache) in the placebo SC × 3 doses treatment group, 1 TEAE (upper respiratory tract infection) in the PF-06823859 300 mg SC × 3 doses treatment group and 1 TEAE (sinusitis) in the PF-06823859 600 mg IV (Q4W) × 2 doses treatment group, none of which were considered by the investigator as treatment related.

One participant experienced a mild localized erythema with induration and tenderness after each of the 100 mg SC dosing with PF-06823859 administered Q2W for a total of 3 doses, but no signs or symptoms of a systemic reaction. These local reactions resolved without further intervention within a few days. This participant also had treatment-induced ADA, which had returned to baseline at the time of discharge ([Section 2.2.2.3](#)).

Overall, there was no apparent difference in the total rate of AEs between the participants treated with PF-06823859 compared to placebo and no apparent dose relationship with the doses of PF-06823859. However, the rate of mild upper respiratory tract infection appears to be higher in participants treated with PF-06823859.

There were no clinically significant observations in ECG, vital signs or laboratory abnormalities.

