8.7. Immunogenicity Assessments

Blood samples of approximately 6 mL, to provide approximately 2 mL serum, will be collected for determination of ADA and NAb as specified in the SoA. Instructions for the collection and handling of biological samples will be provided in the laboratory manual or by the sponsor. The actual date and time (24-hour clock time) of each sample will be recorded.

Samples collected for determination of ADA and NAb may also be used for additional characterization of the immune response and/or evaluation of the bioanalytical method, CCI

Genetic analyses will not be performed on these serum samples unless consent for this was included in the informed consent. Participant confidentiality will be maintained.

Samples will be analyzed using a validated analytical method in compliance with applicable SOPs. Samples tested as ADA positive (not just confirmed positive, but also with a titer positive result) will be further tested for NAb using validated NAb assays.

The immunogenicity samples must be processed and shipped as indicated in the instructions provided to the investigator site to maintain sample integrity. Any deviations from the immunogenicity sample handling procedure (eg, sample collection and processing steps, interim storage, or shipping conditions), including any actions taken, must be documented and reported to the sponsor. On a case-by-case basis, the sponsor may make a determination as to whether sample integrity has been compromised.

Immunogenicity information that would unblind the study will not be reported to investigator sites or blinded personnel until the study has been unblinded.

Any changes in the timing or addition of time points for any planned study assessments must be documented and approved by the relevant study team member and then archived in the sponsor and site study files, but will not constitute a protocol amendment. The IRB/EC will be informed of any safety issues that require alteration of the safety monitoring scheme or amendment of the ICD.

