9.3.3.2. Immunogenicity Analyses

Overall incidence of development of ADA, NAb will be calculated and summarized by treatment and time points specified in the [SoA](#). Participants level immune response will also be summarized by treatment. Effect of positive ADA and neutralizing immune response on safety and PK may be assessed, if appropriate.

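### ADA and NAb incidence is tabulated by dose and visit, but drug is compared with assay tolerance only at the last sample, so drug-masked negatives at earlier visits would go unmarked

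*SAP*

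**What the plan says.** Incidence of ADA and NAb is a secondary endpoint. Protocol 9.3.3.2 states: "Overall incidence of development of ADA, NAb will be calculated and summarized by treatment and time points specified in the" schedule of activities. SAP 6.2.2 carries this out with, among others, a "Summary of incidence of ADA and NAb by dose and time postdose" and a "Summary of cumulative incidence of ADA and NAb by dose and time postdose".

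The same SAP list has one item that compares drug with the tolerance of the ADA assay: "Summary of participants with ADA negative and PK > assay tolerance value at last sampling point". Another item looks at how ADA and NAb status affects concentrations. That concerns the effect of antibody on PK and does not qualify a negative result. Titers are to be listed, and SAP 6.2.1 adds "a listing of all concentrations sorted by subject ID, cohort, dose and nominal time postdose".

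NAb testing follows from the ADA result. Protocol 8.7 states: "Samples tested as ADA positive (not just confirmed positive, but also with a titer positive result) will be further tested for NAb".

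Neither document states the tolerance value, or says how to report an ADA-negative sample taken before the last visit while drug is above tolerance.

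**The concern.** Circulating drug can hide ADA from an assay. The SAP accepts this, because it names ADA-negative with drug above tolerance as a state worth reporting. It looks for that state only where a completer's drug is lowest, yet it counts incidence at every post-dose ADA visit. An earlier negative drawn above tolerance enters the by-time tables as a plain negative, and its NAb is never tested.

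Any such effect depends on dose. Levels at 900 mg stay above a given tolerance longer than at 300 mg, so interference alone could make ADA look less frequent or later at 900 mg. With 5 participants per active arm, one hidden positive moves a visit row by 1/5 = 20 percentage points.

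Transient ADA is the pattern that a last-sample check can miss. Protocol 2.2.2.1 reports one participant (100 mg SC) with "treatment-induced ADA, which had returned to baseline at the time of discharge". That case was detected, not masked. It shows only that ADA to this drug can be transient.

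**Working it through.** **Inputs.** Protocol 2.2.2.2 (earlier healthy-participant study): CL 0.005953-0.006817 L/h, half-life h = 22.73-29.08 days, dose-proportional exposure, AUCinf 5042 (30 mg) to 322,100 µg·h/mL (2000 mg). Doses are 300 and 900 mg, and the last visit is Day 157. Tolerance T is not in the documents and is treated as an assumption over a range.

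**1. Reproduce the stated clearance.** CL = Dose/AUCinf: 30/5042 = 0.00595 L/h (stated minimum 0.005953) and 2000/322,100 = 0.00621 L/h (inside the range). The lowest AUCinf pairs with the lowest CL, so the ranges look like dose-group summaries, not limits for individuals.

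**2. Predicted levels.** One-compartment approximation: C = (Dose/CL) × λ × 2^(−t/h), with λ = ln 2/(24h) per hour and t = study day − 1. Example at 900 mg, CL 0.005953, h = 29.08: λ = 0.000993, starting level 150.2, Day 157 level 150.2 × 2^(−156/29.08) = 3.64 µg/mL. Over the full grid (µg/mL):

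| Day | 300 mg | 900 mg |
|---|---|---|
| 8 | 37.0-51.7 | 111.0-155.2 |
| 15 | 31.3-41.8 | 93.9-125.4 |
| 29 | 22.4-27.3 | 67.3-81.8 |
| 71 | 6.6-9.4 | 19.8-28.3 |
| 157 | 0.48-1.21 | 1.44-3.64 |

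The Day 15 to Day 157 ratio is 2^(142/29.08) = 29.5 to 2^(142/22.73) = 76.0.

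**3. Check against the protocol.** Cav over the second 600 mg Q4W interval = (600/CL)/672 × (1 − 2^(−56/h)) = 96.5-122.8 µg/mL; the protocol reports 109.6. Predicted accumulation, 1 + 2^(−28/h), is 1.43-1.51 against 1.407 reported. That is slightly high, as expected when a bi-phasic profile is approximated by one phase.

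**4. Study day on which drug falls below T:** 1 + ln(C0/T)/(24λ), where C0 is the starting level.

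| Assumed T (µg/mL) | 300 mg | 900 mg |
|---|---|---|
| 5 | 80-98 | 116-144 |
| 10 | 57-69 | 93-115 |
| 20 | 34-40 | 71-86 |
| 50 | by Day 9 | 41-47 |
| 60 | by Day 3 | 34-40 |

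Where both arms cross T during follow-up, the lag is log2(3) × h: 1.585 × 22.73 = 36.0 to 1.585 × 29.08 = 46.1 days.

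**5. How firm the ends are.** Bi-phasic versions built on the same PK give, at 900 mg, Day 15 about 85-121, Day 29 about 51-79 and Day 157 about 1.2-3.5 µg/mL. At T near 60, then, Day 15 is clearly above but Day 29 may not be. At Day 8 the one-compartment maximum is about 155; bi-phasic versions reach about 180.

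At the low end individual spread matters. CL 0.005953 L/h with a 32-day half-life (10% beyond the range) gives 4.65 µg/mL at Day 157. Assuming a mean half-life of 26 days with 20% CV and about 15% CV in volume, about 30% of 900 mg participants exceed 4 µg/mL at Day 157, about 3% exceed 10, and none exceed 67. Moving the mean half-life across 22.73-29.08 days, still at 20% CV, changes the share above 10 to between 0.5% and 8.6%.

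**6. What 5 per arm can show.** The earlier rate was 6/48 = 0.125. An arm of 5 expects 5 × 0.125 = 0.6 positives and has a 0.875^5 = 51% chance of none.

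**Not claimed.** The columns of the schedule row "Immunogenicity (ADA, NAb" are broken in the text available for this review, so no count of affected visits is given.

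**The case against.** The strongest reply is that nothing shows the assay is affected. The tolerance is unknown, and any assumed range is chosen partly because the issue arises inside it. Protocol 2.2.2.3 reports ADA detected at 900 mg IV and at 600 mg IV Q2W, a regimen whose Cav was 181.6 µg/mL. Sampling times are not given, so this does not exclude masking, but it does count against assuming it. This stands, and it is why the point is conditional.

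Second, the last-sample check is the right one for persistent ADA: a response still present at Day 157 is tested when drug is lowest, and a doubtful negative there is flagged. This also stands. It leaves transient ADA and the timing of detection.

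Third, the concentration and titer listings, with the by-sample summary, would let a reader find the affected samples. That is true only for a reader who has the tolerance value, and the incidence tables would still carry unmarked negatives.

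Fourth, the analysis is descriptive, with no hypotheses or decision rules. That bears on priority, not on whether the tables are correctly labelled.

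**Conclusion.** The point holds as a conditional, low-priority improvement. The SAP applies its own interference criterion at one sample and reports incidence at all of them. For an assumed tolerance of about 10-60 µg/mL and typical PK, the by-dose, by-time and cumulative rows could count masked samples as negative, and few or no completers would be flagged at Day 157. The longer exposure at 900 mg applies where both arms cross the tolerance. Near the top of the range 300 mg is hardly affected and 900 mg only at early visits.

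A reader might infer three stronger things that the documents do not support:

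- **That masking will occur, or that ADA at 900 mg will be understated.** Without the tolerance this cannot be said.
- **That the planned check can flag no completer.** This fails near 4-5 µg/mL, where individual variation would put some 900 mg completers above tolerance at Day 157. Early terminators, checked at an earlier last sample, could also be flagged. Below about 0.5 µg/mL the existing check flags every ADA-negative active completer with typical PK.
- **That overall ADA incidence is unreliable.** Final status for persistent ADA is protected.

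The sample size supports no firm dose contrast in either direction, with or without the change.

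**What to change.** In SAP 6.2.2:

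1. Keep the last-sample summary for participant status.
2. Apply the same criterion (ADA negative, drug above tolerance) to each scheduled post-dose ADA sample that has a PK sample from the same visit. Confirm the pairing against the schedule of activities.
3. In the by-dose, by-time tables, show the number of such samples as inconclusive beside positive and negative.
4. Give the tolerance value in a table footnote. The planned last-sample check already requires it.

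This matters for the active arms only. Protocol 6.3.2 says placebo specimens are not routinely analyzed for drug, and no drug is expected in them.

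The cost is a few lines of SAP text and one more column in tables already planned. If pairing is confirmed, no new samples, visits or participants are needed. The downside is fewer conclusive samples at early visits, especially at 900 mg. At an assumed 10 µg/mL, for example, ADA-negative 900 mg samples would typically be inconclusive until about Day 93-115.

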6.3. Other Endpoint(s)

N/A

6.4. Subset Analyses

No subset analysis will be conducted for this study.

6.5. Baseline and Other Summaries and Analyses

6.5.1. Baseline Summaries

Demographic and baseline characteristics (age, sex, ethnicity, race, weight, body mass index and height) collected prior to the first dose of the study drug will be summarized following the CaPS.

6.5.2. Study Conduct and Participant Disposition

The following participant dispositions will be summarized.

- A summary of participant discontinuations up to end of study;
- Summary of participant dispositions analyzed for PK, immunogenicity, as well as for safety;
- Summary of numbers of participant treated by treatment group.

Data will be reported following the CaPS.

6.5.3. Study Treatment Exposure

Study treatment exposure will be listed.

[figure not shown]
6.5.4. Concomitant Medications and Nondrug Treatments

All concomitant medications as well as nondrug treatments will be summarized following the CaPS.

6.6. Safety Summaries and Analyses

The details of safety analyses are described in the Section [6.1](#).

PFIZER GENERAL BUSINESS

[figure not shown]

7. INTERIM ANALYSES

No formal interim analysis will be conducted for this study. As this is a sponsor-open study, the sponsor may conduct unblinded reviews of the data during the course of the study for the purpose of safety assessment, facilitating PK/PD modeling, and/or supporting clinical development.

PFIZER GENERAL BUSINESS

A large rectangular area of the page is redacted with black ink, obscuring several lines of text.

8. APPENDICES

Appendix 1. Categorical Classes for Vital Signs and ECG of Potential Clinical Concern

Categories for Vital Signs

Systolic BP (mm Hg)	min. <90	
Diastolic BP (mm Hg)	min. <50	
Pulse rate (bpm)	min. <40	max. >120
Systolic BP (mm Hg) change from baseline	max. increase ≥ 30	max. decrease ≥ 30
Diastolic BP (mm Hg) change from baseline	max. increase ≥ 20	max. decrease ≥ 20

Categories for PR and QRS

PR (ms)	max. ≥ 300
QRS (ms)	max. ≥ 140
PR (ms) increase from baseline	Baseline >200 and max. $\geq 25\%$ increase or Baseline ≤ 200 and max. $\geq 50\%$ increase
QRS (ms) increase from baseline	$\geq 50\%$ increase

Categories for QT

[figure not shown]
Absolute value	≥ 500
----------------	------------

Categories for QTcF

Degree of Prolongation	Mild (msec)	Moderate (msec)	Severe (msec)
Absolute value	≥ 450 and <480	≥ 480 and <500	≥ 500
Increase from baseline		≥ 30 and <60	≥ 60

Measurements that fulfill these criteria are to be listed in report.

PFIZER GENERAL BUSINESS

Appendix 2. List of Abbreviations

Abbreviation	Term
ADA	antidrug antibodies
AE	adverse event
AUC	area under the curve
AUC _{14day}	AUC from time 0 to 14 days post-dose
AUC _{28day}	AUC from time 0 to 28 days post-dose
AUC _{extrap%}	percent of AUC _{inf} based on extrapolation
AUC _{inf}	AUC from time 0 extrapolated to infinite time
AUC _{last}	AUC from time 0 to the time of the last quantifiable concentration
BLQ	below the limit of quantitation
CaPS	CDISC and Pfizer Standards
CDISC	Clinical Data Interchange Standards Consortium
C _{max}	maximum observed concentration
CL	clearance
CRF	case report form
CRU	clinical research unit
dn	dose normalized
ECG	electrocardiogram
HR	heart rate
IRR	infusion related reaction
IV	intravenous(ly)
k _{el}	terminal phase rate constant
LLQ	lower limit of quantitation
MRT	mean residence time
N/A	not applicable
NAb	neutralizing antibodies
NC	not calculated
ND	not done
NS	no sample
PD	pharmacodynamic(s)
PK	pharmacokinetic(s)
PR	pulse rate
PT	preferred term
QTc	corrected QT
QTcF	corrected QT (Fridericia method)
SAE	serious adverse event
SAP	statistical analysis plan
SD	standard deviation
SOC	system organ class

PFIZER GENERAL BUSINESS

Abbreviation	Term
$t_{1/2}$	terminal phase half-life
TEAE	treatment-emergent adverse event
TME	targeted medical event
T_{max}	time to reach C_{max}
V_{ss}	volume at steady state

PFIZER GENERAL BUSINESS
